The maintenance period includes an “escape arm” for participants whose EASI response suggests the need for a higher dose. The escape therapy is LY3454738 CCI mg CCI.

A participant will receive this escape therapy under the conditions listed here.

Begin LY3454738 CCI mg CCI as escape therapy...	if the participant...
At Week 16	has not achieved an CCI response at Week 16.
At Weeks CCI	has not achieved an CCI response at Weeks CCI

A participant receiving escape therapy will continue receiving escape therapy through the last dosing visit of the study (Week CCI unless the participant is discontinued from study intervention).

Topical rescue medication in the maintenance period is permitted from Week CCI until the end of the study for participants who do not achieve an CCI response, as described in Section 6.9.1.

Posttreatment follow-up period

All participants are expected to have 2 follow-up visits after the last dosing visit, as listed here.

Condition	First follow-up visit	Second follow-up visit
If the participant did not discontinue study intervention early...	occurs approximately 8 wk after last dosing visit	occurs approximately 12 wk after last dosing visit
If the participant did discontinue study intervention early...	occurs after ED and with an approximately 8-week interval between the last dose and this visit	occurs after ED and with an approximately 12-week interval between the last dose and this visit

Blinding

This study design includes investigator and participant blinding (masking) (Section 6.4). Blinding of the participant's original induction and maintenance treatments will continue until all participants have completed their last posttreatment follow-up visit or have discontinued the study. All blinded assessments and sample collections should be completed before a dose is administered at the dosing visits.

Internal assessment committee

During the study, an IAC will review the safety data in an unblinded fashion, as described in the master IMMB protocol, Appendix 1, Section 10.1.5.

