4.4. Secondary Endpoints/Estimands Analysis

The MP-SAP will focus on two safety analyses: (1) overall safety profile across treatment periods including posttreatment follow-up, and (2) safety profile during induction. The ISA-SAP will define the treatment groups, if relevant, for the overall and induction safety analyses.

Please see Section 4.4 of the relevant ISA-SAP for secondary endpoints and/or estimands for efficacy analyses or ISA-specific safety analyses.

Estimand for overall safety analyses

A secondary clinical question of interest is: what is the difference between active study intervention versus placebo in the number, percent, and/or incidence rates (IRs) of treatment-emergent adverse events (TEAEs) of interest?

The estimand is described by the following attributes:

- Population: participants with moderate-to-severe AD
- Endpoint(s): number, percent, and/or IRs for first TEAEs of interest
- How to account for intercurrent events:
 - Early Permanent Discontinuation of Study Intervention: TEAEs during the posttreatment follow-up will be considered attributable to the study intervention
 - Use of Prohibited or Rescue Medication: TEAEs after the use of prohibited or rescue medication will be considered attributable to the study intervention.

- Assignment to Escape Arm (if applicable): if a participant escapes from placebo to active study intervention, subsequent TEAEs will be attributable to the active study intervention, and
- Assignment to Placebo Withdrawal Arm (if applicable): if a participant is re-randomized from active study intervention to placebo, TEAEs will be considered attributable to the active study intervention until the completion of the study
- Population-level summary: the difference in IRs for TEAEs of interest between participants receiving (rather than assigned to) active study intervention versus placebo, and
- Rationale for estimand:
 - TEAEs of interest for participants receiving active study intervention are considered attributable to study intervention

CCI

- the use of prohibited or rescue medication are potential components of treatment regimens and should therefore be attributable to study intervention.

Secondary estimand for safety during induction period

A secondary clinical question of interest is: what is the difference between the active study intervention versus placebo (or active comparator) in the number, percent, and/or IRs of TEAEs of interest during the induction treatment period?

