Laboratory tests and vitals (overall safety analyses)	
Randomized in the initial period: The last available value prior to the first dose of study drug.
 
Assigned to Escape Arm from Placebo (if applicable): The last available value prior to the first dose of active study intervention on the escape arm.
	
For participants randomized to active study intervention in the initial period or assigned to escape arm from placebo: Starts at the time of first dose of the active study intervention and ends at the earliest of the following:
 
 • Time of discontinuation from ISA • Time of ISA completion, or • Database cut-off date for ongoing studies. 
For participants initially randomized to placebo: Starts at the time of first dose and ends at the earliest of the following:
 
 • Time of discontinuation from ISA • Time of ISA completion • Time of first dose on the escape arm (if applicable), or • Database cut-off date for ongoing studies.

Abbreviations: ISA = intervention specific appendix; TEAE = treatment-emergent adverse event.

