4.6.2. Adverse Events

Adverse events (AEs) are recorded in the electronic case report form (eCRF). Each AE will be coded to System Organ Classes (SOC) and Preferred Terms (PT), using the Medical Dictionary for Regulatory Activities (MedDRA) version that is current at the time of the database lock. Severity of AEs is recorded as mild, moderate, or severe.

TEAEs are defined as events that either first occurred or worsened in severity during the postbaseline period defined in [Table 4.1](#). The MedDRA Lowest Level Terms will be used in defining which events are treatment-emergent (TE). The maximum severity for each Lowest Level Term during the baseline period will be used as baseline. TE status in the presence of incomplete data will be determined through the following rules:

- if an AE has missing severity during the baseline period, then the baseline severity will be considered mild for determining TE status
- AEs with missing severity during the postbaseline period will be considered TE regardless of severity during the baseline period, and
- AEs with insufficient data on start date to determine the relevant period (for example, AE start year is the same as the treatment start year, but the AE start month and day are missing) will be considered TE.

For AEs occurring on the first day of the postbaseline period, the day and time of the AE start date will be compared with the dosing day and time. If such a comparison cannot be made due to incomplete day and time information, the AE will be considered TE.

Summaries of TEAE data will at a minimum include

- the number of participants in the safety population of interest
- the number of participants experiencing the event in the safety population of interest, and
- frequency, or percentage, relative to the safety population of interest.

As noted in [Table 4.2](#), some TEAE analyses will also include:

- person-years at-risk during the postbaseline period (years from start of postbaseline period to the first event of interest or the end of the postbaseline period, whichever is first), and
- (exposure-adjusted) IRs and corresponding confidence intervals.

For events that are sex specific, the denominator, computation of percentage, and IR will only include participants of the given sex.

System Organ Class mapping

MedDRA PTs are assigned to a SOC through primary mappings (defined by MedDRA). Thus, MedDRA PTs will appear in only 1 SOC.

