Participants with elevated or low values meeting specified levels	
Excludes analytes collected qualitatively.
 
Definitions of low and high values in Tables 59 and 60 from FDA's Standard Safety Tables and Figures Integrated Guide will be used for the numerator^a.
 
Includes participants with at least 1 postbaseline measurement.
 
Maximum baseline is used for elevated assessments and minimum baseline is used for low assessments.
 
See Table 24 from FDA's Standard Safety Tables and Figures Integrated Guide^a.
	Overall Analysis
Listing of abnormal laboratory findings	
Includes laboratory analytes collected quantitatively (high or low during postbaseline using Level 2 definitions; see FDA's Standard Safety Tables and Figures Integrated Guide^a) and qualitatively (abnormal during postbaseline).
 
Includes participant identification, treatment group, laboratory analyte collection day (that is, days from start of study intervention), analyte name, and analyte finding.
	Overall Analysis

Abbreviations: SD = standard deviation; SI = international system of units.

^a CDER/BIRRS 2022.

Scatter plots to support clinical laboratory evaluations

Scatter plots of maximum-by-maximum measurements and minimum-by-minimum measurements will not be created a priori. They may be created if warranted after review of the planned tables and figures, using Figures 6.3 and 6.4 from the Analysis and Displays for Labs white paper (PHUSE 2022) as the model. Analysis Data Model datasets will include variables to enable the creation of scatter plots for use in either an interactive tool or for ad hoc figures.

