4.6.5.3. Hepatic Safety

Hepatic labs include alanine aminotransferase, aspartate aminotransferase, total bilirubin, direct bilirubin, serum alkaline phosphatase, international normalized ratio, and gamma-glutamyltransferase. When criteria are met for hepatic evaluations, investigators will conduct close monitoring of hepatic symptoms and liver tests, perform a comprehensive evaluation for alternative causes of abnormal liver tests, and complete follow-up hepatic safety eCRFs.

[Table 4.5](#) describes the planned summary tables related to hepatic safety.

Table 4.5. Summary Tables and Figures Related to Hepatic Safety

Analysis	Sample
Abnormal Postbaseline Categories – Hepatic Safety Parameters 
 ALT: The number and percentage of participants with a measurement greater than or equal to 1 time (1X), 3 times (3X), 5 times (5X), 10 times (10X), and 20 times (20X) the performing lab ULN during the treatment period for all participants with a postbaseline value. AST: The number and percentage of participants with a measurement greater than or equal to 1 time (1X), 3 times (3X), 5 times (5X), 10 times (10X), and 20 times (20X) the performing lab ULN during the treatment period for all participants with a postbaseline value. ALP: The number and percentage of participants with a measurement greater than or equal to 2 times (2X), and 3 times (3X) the performing lab ULN during the treatment period will be summarized for all participants with a postbaseline. TBL: The number and percentage of participants with a measurement greater than or equal to 2 times (2X), 5 times (5X), and 8 times (8X) the performing lab ULN during the treatment period will be summarized for all participants with a postbaseline value. DBL: The number and percentage of participants with a measurement greater than or equal to 2 times (2X) and 5 times (5X) the performing lab ULN during the treatment period will be summarized for all participants with a postbaseline value. GGT: The number and percentage of participants with a measurement greater than or equal to 2 times (2X) the performing lab ULN during the treatment period will be summarized for all participants with a postbaseline value. 	Overall Analysis
Hepatocellular Drug-Induced Liver Injury Screening Plot (TBL vs. ALT or AST)	Overall Analysis
Cholestatic Drug-Induced Liver Injury Screening Plot (TBL vs. ALP)	Overall Analysis

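### SAP Table 4.5 counts liver-test elevations without reference to baseline, so elevations that began before LY3454738 and persist after its first dose count as events on drug

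*SAP*

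**What the plan says.** SAP Section 4.6.5.3, Table 4.5, lists ULN multiples for ALT, AST, ALP, total bilirubin, direct bilirubin and GGT. For ALT and AST the rule is a measurement at or above a multiple of "the performing lab ULN during the treatment period for all participants with a postbaseline value", with multiples starting at 1x. The other four analytes follow the same pattern, starting at 2x. The sample is the Overall Analysis. No row sets a baseline condition, splits by baseline, or says what happens when baseline is missing.

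Other parts of the SAP do use baseline:

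- Table 4.1 gives a laboratory baseline. For placebo participants who escape it is "The last available value prior to the first dose of active study intervention on the escape arm". The LY window for them, and for those randomised to LY, is one that "Starts at the time of first dose of the active study intervention and ends at the earliest of the following" of ISA discontinuation, ISA completion or data cut-off.
- Table 4.3, on elevated or low laboratory values, says "Maximum baseline is used for elevated assessments and minimum baseline is used for low assessments".
- Section 4.6.2 says "TEAEs are defined as events that either first occurred or worsened in severity during the postbaseline period", and sets the reference: "The maximum severity for each Lowest Level Term during the baseline period will be used as baseline".

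Escape to LY exists in this trial. Protocol Section 4.1 states: "The maintenance period includes an “escape arm” for participants whose EASI response suggests the need for a higher dose". The response threshold that triggers it is redacted. For adverse events, SAP Section 4.4 adds that "if a participant escapes from placebo to active study intervention, subsequent TEAEs will be attributable to the active study intervention".

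**The concern.** A table of postbaseline abnormalities is naturally read as showing what happened on treatment. Without a baseline reference, a participant whose ALT was above the ULN before the first dose, and stayed there, looks the same as one whose ALT rose on drug.

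This has two consequences. Elevations present at randomisation should be similar in both groups, so they add a common background and make a real difference harder to see. Elevations present when a placebo participant escapes are different: they can move only from placebo to LY, and a persistent one can appear in both groups. At stake is how clearly the main hepatic summary separates existing from new elevations.

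**Working it through.** The documents state no figure on this point, so there is none to reproduce. The check is textual, followed by an illustration on declared assumptions.

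**1. Text.** Take a placebo participant with ALT at 1.2x ULN at Week 16 who then escapes.
- Under Table 4.1 the Week 16 value is the pre-escape baseline, and the LY window opens at the first LY dose.
- Table 4.5 does not use that baseline. If the next ALT is still at or above 1x ULN, the participant counts under LY.
- If any value after the first placebo dose and before escape was at or above 1x ULN, the participant also counts under placebo.
- If ALT is below 1x ULN at every measurement after the first LY dose, there is no LY count.

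**2. Inputs.**
- From Protocol Section 4.1: 96 + 68 + 28 = 192 LY and 68 placebo.
- Assumed: share at or above 1x ULN before the first dose, b = 5% to 20%; share of elevations persisting into the next window, s = 60% to 80%; new elevations on placebo, i = 8%.
- Assumed escapees: 34 (50% of 68) to 60. The high figure is 68 x 0.88 = 59.8, from the 12% placebo EASI-75 rate in Protocol Section 9.5. It would apply at Week 16 only if the redacted threshold were EASI-75 and every nonresponder stayed on treatment.

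**3. Randomised LY participants counted with no new elevation: 192 x b x s.**
- Low: 192 x 0.05 x 0.6 = 5.8
- High: 192 x 0.20 x 0.8 = 30.7

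**4. Escapees counted under both groups: E x [b x s + (1 - b) x i] x s.** The bracket is the share counted on placebo; the last factor is persistence after the first LY dose.
- Low: 34 x (0.030 + 0.076) x 0.6 = 2.2
- High: 60 x (0.160 + 0.064) x 0.8 = 10.8

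Together that is about 8 of 226 (3.5%) to 41 of 252 (16.5%) in the LY column. A row limited to participants below threshold at baseline would contain none of them.

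**5. Dilution in the randomised comparison (68 v 192, no escapees).** Suppose LY truly doubles new elevations, from 8% to 16%. The rate as written is b x s + (1 - b) x i. The restricted rate is i, with group sizes multiplied by (1 - b). z is the difference over the unpooled standard error, with s = 0.8.
- b = 10%, as written: 0.08 + 0.90 x 0.08 = 15.2% v 0.08 + 0.90 x 0.16 = 22.4%; z = 0.072 / 0.0529 = 1.36
- b = 10%, restricted (61.2 v 172.8): 8% v 16%; z = 0.080 / 0.0445 = 1.80
- b = 20%, as written: 22.4% v 28.8%; z = 1.06
- b = 20%, restricted (54.4 v 153.6): z = 1.69

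The restricted row has the better signal-to-noise ratio despite its smaller denominator. The z values serve only as that measure; the SAP plans no safety p-values unless the ISA-SAP asks for them.

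**The case against.** The strongest reply is that Table 4.5 is a screening display. It sits beside two drug-induced liver injury screening plots, and counting every abnormal value whatever the baseline is a recognised choice for that purpose. The vital-signs threshold rule in Table 4.4 states no baseline condition either. This stands, and it is why the existing rows should stay.

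Second, other displays help. ALT, AST, ALP and bilirubin are in Table 6.3, so Table 4.3 gives change-from-baseline plots and an elevated-value table that uses baseline. This stands in part. Table 6.3 does not name GGT or direct bilirubin, and maximum baseline is unclear when Table 4.1 reduces the laboratory baseline to one last value.

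Third, the ISA-SAP may clarify or add analyses, and it was not supplied. A reader might infer from the Overall Analysis label that no induction version of the hepatic table will exist. The master SAP specifies none, but these documents cannot settle what the ISA-SAP contains.

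Fourth, the illustration rests on assumed rates. Some laboratory eligibility criteria are in the master protocol, also not supplied, so baseline prevalence cannot be judged. Sixty escapees is a high case, since the 12% response rate treats discontinuation as nonresponse and those who stopped cannot escape. Later escape points work the other way, with 68 as the ceiling. All of this stands.

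**Conclusion.** The gap is real but limited. Table 4.5 ignores a baseline that the same SAP defines, so an elevation that predates LY is counted under LY when a value after the first LY dose still meets the threshold. For placebo escapees the same elevation can count in both groups, and that transfer runs in one direction only.

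Two stronger readings are not supported. One is that every elevation on placebo is counted again under LY; that requires a later value still at threshold. The other is that the table is biased against LY throughout, or conceals a hepatic effect. Elevations present at randomisation affect both groups and dilute rather than bias. Escapees join the LY denominator as well as the numerator, so the change in the LY percentage depends on how their rate compares with that of randomised LY participants. Table 4.3 and the screening plots also remain.

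The effect should lie mainly in the 1x ULN rows for ALT and AST, on the assumption that few participants enter with larger elevations. The counts of about 6 to 31 randomised LY participants and 2 to 11 escapees depend wholly on the assumed prevalence, persistence, placebo rate and number of escapees.

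**What to change.** In SAP Table 4.5:

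- Keep the all-participant rows as the screening display.
- Add a split by baseline category: below the threshold, at or above it, and missing. Do this at least for ALT and AST at 1x ULN, and preferably for every analyte and threshold.
- State whether last or maximum baseline defines the category, and reconcile this with Tables 4.1 and 4.3.
- For placebo participants counted under LY after escape, use the Table 4.1 baseline before the first LY dose.
- Replace the treatment-period wording with the Table 4.1 postbaseline window, so that it is clear which values belong to placebo, which to LY, and whether follow-up is included.

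The cost is SAP wording and a few extra rows. No new data are needed: chemistry is taken at Week 0 and Week 16, before dosing unless otherwise specified. Denominators in the split rows will be slightly smaller. For participants who escape later, the last chemistry value may be some weeks old, because maintenance chemistry is not taken at every visit.

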4.6.5.4. Infections

For each reported AE of infection, investigators will complete a Follow-Up Form. The form solicits additional information about the reported infections, including details about the laboratory data and clinical specimens used in making the diagnosis; this additional information

facilitates a more thorough medical review and aids in understanding of individual cases, including the strength of the diagnosis. Prior to database lock, reported infection AEs will be coded to PTs, using all the PTs from the Infections and Infestations SOC as defined in MedDRA.

TE confirmed opportunistic infections (OIs) will be identified in a step-wise manner:

1. Identify potential TE OIs
 - a. PTs corresponding to potential TE OIs are listed in a document separate from this SAP. The list is updated with each new version of MedDRA. When the PT list is updated based on new versions of MedDRA, this will not necessitate an update to this SAP. The PT lists are maintained through a separate process.
2. Prior to the database lock, GPS and medical will review the infection-specific CRF and determine whether a potential TE OI qualifies as a confirmed TE OI. TE infections meeting modified criteria for OIs from Winthrop et al. (2015) will qualify as a confirmed TE OI. The modified Winthrop criteria is:
 - a. Candidiasis infections involving the oral cavity and pharynx are not considered OIs. For such an event to be classified as an OI, diagnostic evidence must confirm infection of either the esophagus or GI tract below the esophagus.
 - b. Localized herpes zoster infections are not considered OI. Only multidermatomal infections, disseminated infections, or both are considered OI.
 - i. Localized or nonmultidermatomal are defined as involvement of the primary and/or adjacent dermatomes only. These may be complicated or uncomplicated:
 1. Complicated: documented ocular (cornea or deeper structure; for example, iritis, keratitis, retinitis, and so on) or motor nerve involvement (for example, palsy). Postherpetic neuralgia does not meet criteria for motor nerve involvement.
 2. Uncomplicated: localized or nonmultidermatomal cases that are not complicated.
 - ii. Multidermatomal is defined as involvement beyond primary and adjacent dermatomes (that is, 4 or more contiguous dermatomes) or involvement of 2 or more noncontiguous dermatomes. These may be complicated or uncomplicated.
 1. Complicated: documented ocular (cornea or deeper structure; for example, iritis, keratitis, retinitis, and so on) or motor nerve development.
 2. Uncomplicated: multidermatomal cases.
 - iii. Disseminated: systemic infection, visceral, or widespread cutaneous (for example, 5 or more dermatomes or from 3 to 4 dermatomes including at least 1 noncontiguous [nonadjacent]).
 - c. TE, active tuberculosis infection is an OI.

Table 4.6 describes the planned summary tables related to infection safety.

Table 4.6. Summary Tables, Figures, and Listings Related to Infection Safety

Analysis	Details	Sample
Summary of TE Infections	The number and percent of participants with ≥ 1 TE infection, serious infection (death or SAE), temporary or permanent discontinuation of study intervention due to infection, TE OI, and TE infections of interest.	Induction and Overall Analyses
TE Infections – Infections of Interest	The number of participants, percent of participants, and IRs for participants with ≥ 1 TE infection of interest, maximum severity, serious infection (death or SAE), temporary or permanent discontinuation of study intervention, and whether the event is ongoing or resolved. TE infections of interest: upper respiratory infection, herpes zoster, other herpes infections, conjunctivitis, and candida.	Induction Analysis
Listing of Serious Infections	Includes participant identification, treatment group, SOC/PT, event start date, severity, action taken, relationship to study treatment or non-study treatment, and whether the SAE caused discontinuation.	--
Listing of TE OIs	Includes participant identification, treatment group, SOC/PT, event start date, severity, action taken, relationship to study treatment or non-study treatment, and whether the SAE caused discontinuation.	--

Abbreviations: TE = treatment-emergent; OI = opportunistic infection; IR = incidence rate; SOC = System Organ Class; PT = Preferred Term; SAE = serious adverse event.

